## 8.3. Patients/Subjects Lost to Follow-up

The investigator will consider a patient lost to follow-up if they repeatedly miss scheduled visits and cannot be contacted by the study site. Site personnel are expected to make diligent attempts to contact patient who miss scheduled visits or were otherwise unable to be followed up by the site.

## 9. Study Assessments and Procedures

Section 2 lists the Schedule of Activities, detailing the study procedures and their timing (including tolerance limits for timing).

[Appendix 2](#) lists the laboratory tests that will be performed for this study.

[Appendix 5](#) provides a summary of the maximum number and volume of invasive samples, for all sampling, during the study.

Unless otherwise stated in subsections below, all samples collected for specified laboratory tests will be destroyed within 60 days of receipt of confirmed test results. The investigator or sponsor may retain certain samples for a longer period, if necessary, to comply with applicable laws, regulations, or laboratory certification standards.

### 9.1. Efficacy Assessments

The following efficacy measures will be collected at the times shown in the Schedule of Activities.

- Change in HbA1c from baseline to prespecified time points.
- Change in weight from baseline to prespecified time points. Site personnel will measure weight in a consistent manner using a calibrated scale according to the Schedule of Activities (Section 2). Patients will be weighed in light clothing at approximately the same time in the morning before dosing and after an overnight fast and evacuation of the bowels and the bladder, if possible. During the treatment period, weight will be measured twice on each scheduled occasion, with the patient stepping off the scale between measurements. The personnel will record both weight measurements in the source document and the eCRF. Whenever possible, patients will use the same scale for all weight measurements throughout the study.
- Fasting serum glucose level measured in the central laboratory (actual values and change from baseline to predefined time points).
- 7-point SMPG profile (actual values and change from baseline to pre-specified time points). Patients will be asked to perform 7-point SMPG profiles over a 24-hour period, on nonconsecutive days, according to the Schedule of Activities. The 7-point profile consists of pre-meal and 2-hour postprandial SMPG measurements for the morning, midday, and evening meals in 1 day, and at bedtime. Pre-meal measurements should be taken before the patient begins eating the meal. Patients should record their glucose measurements in their patient diaries, which are considered source documents and are to

be returned to the investigator at each study visit. Values from the 7-point SMPG profile will be transferred from the diary and recorded on the eCRF.

## 9.2. Adverse Events

Investigators are responsible for monitoring the safety of patients who have entered this study and for alerting Lilly or its designee to any event that seems unusual, even if this event may be considered an unanticipated benefit to the patient. The investigator will record all relevant AE/SAE information in the CRF.

The investigator is responsible for the appropriate medical care of patients during the study.

Investigators must document their review of each laboratory safety report.

The investigator remains responsible for following, through an appropriate health care option, AEs that are serious or otherwise medically important, considered related to the IP or the study, or that caused the patient to discontinue the IP before completing the study. The patient should be followed up until the event resolves, stabilizes with appropriate diagnostic evaluation, or is reasonably explained. The frequency of follow-up evaluations of the AE is left to the discretion of the investigator.

After the ICF is signed, study site personnel will record, via eCRF, the occurrence and nature of each patient's preexisting conditions, including clinically significant signs and symptoms of the disease under treatment in the study. Additionally, site personnel will record any change in the condition(s) and the occurrence and nature of any AEs.

The investigator will interpret and document whether or not an AE has a reasonable possibility of being related to study treatment, or a study procedure, taking into account the disease, concomitant treatment, or pathologies.

A "reasonable possibility" means that there is a potential cause and effect relationship between the IP, study device, and/or study procedure and the AE.

Planned surgeries should not be reported as AEs unless the underlying medical condition has worsened during the course of the study.

If a patient's IP is discontinued as a result of an AE, study site personnel must report this to Lilly or its designee via eCRF.

### **9.2.1. Serious Adverse Events**

An SAE is any AE from this study that results in 1 of the following:

- death
- initial or prolonged inpatient hospitalization
- a life-threatening experience (that is, immediate risk of dying)
- persistent or significant disability/incapacity
- congenital anomaly/birth defect
- important medical events that may not be immediately life-threatening or result in death or hospitalization but may jeopardize the patient or may require intervention to prevent 1 of the other outcomes listed in the definition above.

Study site personnel must alert the Lilly CRP/CP, or its designee, of any SAE as soon as practically possible.

Additionally, study site personnel must alert Lilly Global Patient Safety, or its designee, of any SAE within 24 hours of investigator awareness of the event via a sponsor-approved method. If alerts are issued via telephone, they are to be immediately followed up with official notification on study-specific SAE forms. This 24-hour notification requirement refers to the initial SAE information and all follow-up SAE information.

Although all AEs are recorded in the eCRF after signing informed consent, SAE reporting to the sponsor begins after the patient has signed informed consent and has received IP. However, if an SAE occurs after signing informed consent, but prior to receiving IP, AND is considered Reasonably Possibly Related to a study procedure then it MUST be reported.

Investigators are not obligated to actively seek AEs or SAEs in subjects once they have discontinued from and/or completed the study (the patient's summary eCRF has been completed). However, if the investigator learns of any SAE, including a death, at any time after a patient has been discharged from the study, and he/she considers the event reasonably possibly related to the study treatment or study participation, the investigator must promptly notify Lilly.

Pregnancy (maternal or paternal exposure to IP) does not meet the definition of an AE. However, to fulfill regulatory requirements, any pregnancy should be reported following the SAE process to collect data on the outcome for both mother and fetus.

### **9.2.1.1. Suspected Unexpected Serious Adverse Reactions**

Suspected unexpected serious adverse reactions (SUSARs) are serious events that are not listed in the IB and that the investigator reports as related to IP or procedure. Lilly has procedures that will be followed for the recording and expedited reporting of SUSARs that are consistent with global regulations and the associated detailed guidances.

### **9.2.2. Complaint Handling**

Lilly collects product complaints on IPs and drug delivery systems used in clinical trials to ensure the safety of study participants, monitor quality, and to facilitate process and product improvements.

Patients should be instructed to contact the investigator as soon as possible if he or she has a complaint or problem with the IP (or drug delivery system) so that the situation can be assessed.

## **9.3. Treatment of Overdose**

For the purposes of this study, an overdose of tirzepatide is considered any dose higher than the dose assigned through randomization.

Refer to the IB for tirzepatide.

## **9.4. Safety**

### **9.4.1. Laboratory Tests**

For each patient, laboratory tests detailed in [Appendix 2](#) should be conducted according to the Schedule of Activities (Section 2).

### **9.4.2. Vital Signs**

For each patient, vital sign measurements should be conducted according to the Schedule of Activities (Section 2).

Blood pressure and pulse rate should be measured after approximately 5 minutes in the supine position.

If orthostatic measurements are required, patients should be supine for approximately 5 minutes and stand for at least 2 minutes. If the patient feels unable to stand, personnel will record only the supine vital signs.

Unscheduled orthostatic vital signs should be assessed, if possible, during any AE of dizziness or posture-induced symptoms. If warranted, site personnel may measure additional vital signs during each study period.

Body temperature will be measured as specified in the Schedule of Activities and as clinically indicated (Section 2).

#### **9.4.3. *Electrocardiograms***

For each patient, 12-lead digital ECGs should be collected according to the Schedule of Activities (Section 2).

Site personnel should report any clinically significant findings from ECGs that result in a diagnosis and occur after the patient receives the first dose of the IP to Lilly, or its designee, as an AE via eCRF.

For each patient, personnel will collect a single 12-lead digital ECG at screening and follow-up or early termination visit according to the Schedule of Activities (Section 2). Electrocardiograms may be obtained at additional times, when deemed clinically necessary. The investigational site should store all ECGs recorded.

Electrocardiograms must be recorded before collecting any blood samples for safety or PK tests. Patients must be supine for approximately 5 to 10 minutes before ECG collection and remain supine but awake during ECG collection.

At the site, a qualified physician (the investigator or qualified designee) will interpret ECGs as soon as possible. Ideally, ECG interpretation will occur while the patient is still present to determine whether the patient meets entry criteria at the relevant visit(s) and for immediate patient management, should any clinically relevant findings be identified.

If a clinically significant quantitative or qualitative change from baseline is identified (including, but not limited to, changes in QT interval/QT interval corrected for heart rate using Fridericia's formula from baseline) after enrollment, the investigator will assess the patient for symptoms (for example, palpitations, near syncope, syncope) to determine whether the patient can continue in the study. The investigator or qualified designee is responsible for determining if any change in patient management is needed and must document their review of the ECG printed at the time of evaluation from at least 1 of the replicate ECGs from each time point. Any new clinically relevant finding should be reported as an AE.

#### **9.4.4. Safety Monitoring**

The Lilly clinical pharmacologist or CRP/scientist will monitor safety data throughout the course of the study.

Lilly will review SAEs within time frames mandated by company procedures. The Lilly clinical pharmacologist, CRP, or CRS will periodically review the following data:

- trends in safety data
- laboratory analytes
- AEs including GI events, hypoglycemia, injection-site reactions, hypersensitivity reactions, and pancreatitis

When appropriate, the Lilly clinical pharmacologist, CRP, or CRS will consult with the functionally independent Global Patient Safety therapeutic area physician or CRS.

##### **9.4.4.1. Hepatic Safety**

If a study patient experiences elevated ALT  $\geq 3X$  ULN, ALP  $\geq 2X$  ULN, or elevated TBL  $\geq 2X$  ULN, liver tests ([Appendix 4](#)) should be repeated within 3 to 5 days including ALT, AST, ALP, TBL, direct bilirubin, gamma-glutamyl transferase, and creatine kinase to confirm the abnormality and to determine if it is increasing or decreasing. If the abnormality persists or worsens, the investigator should initiate clinical and laboratory monitoring based on consultation with the Lilly clinical pharmacologist, CRP, or CRS. Monitoring should continue until levels normalize and/or are returning to approximate baseline levels.

Additional safety data should be collected if 1 or more of the following conditions occur:

- elevation of serum ALT to  $\geq 5X$  ULN on 2 or more consecutive blood tests
- Elevation of serum TBL to  $\geq 2X$  ULN (except for cases of known Gilbert's syndrome)
- elevation of serum ALP to  $\geq 2X$  ULN on 2 or more consecutive blood tests
- patient/subject discontinued from treatment due to a hepatic event or abnormality of liver tests
- hepatic event considered to be an SAE.

#### 9.4.4.2. Pancreatic Safety

Acute pancreatitis is defined as an AE of interest in all trials with tirzepatide including this trial. Acute pancreatitis is an acute inflammatory process of the pancreas that may also involve peripancreatic tissues and/or remote organ systems (Banks and Freeman 2006). The diagnosis of acute pancreatitis requires 2 of the following 3 features:

- abdominal pain, characteristic of acute pancreatitis (generally located in the epigastrium and radiates to the back in approximately half the cases [Banks and Freeman 2006; Koizumi et al. 2006]; the pain is often associated with nausea and vomiting)
- serum amylase (total and/or pancreatic) and/or lipase  $\geq 3X$  ULN
- characteristic findings of acute pancreatitis on computed tomography (CT) scan or magnetic resonance imaging (MRI)

If acute pancreatitis is suspected, appropriate laboratory tests (including levels of pancreatic amylase [p-amylase] and lipase) should be obtained via the local laboratory. Imaging studies, such as abdominal CT scan with or without contrast, MRI, or gallbladder ultrasound, should be performed. If laboratory values and/or abdominal imaging support the diagnosis of acute pancreatitis, the patient must discontinue therapy with investigational product, but will continue in the study on another glucose-lowering regimen (details on rescue intervention will be provided). The most appropriate diabetes therapeutic regimen will be decided by the investigator, based on the patient's clinical status. A review of the patient's concomitant medications should be conducted to assess any potential causal relationship with pancreatitis.

Each case of an AE of pancreatitis must be reported. If typical signs and/or symptoms of pancreatitis are present and confirmed by laboratory values (lipase or amylase [total and/or pancreatic]) and imaging studies, the event must be reported as an SAE. For a potential case that does not meet all of these criteria, it is up to the investigator to determine the seriousness of the case (AE or SAE) and the relatedness of the event to study drug.

Each patient will have measurements of p-amylase and lipase (assessed at the local laboratory) as shown on the Schedule of Activities (Section 2) to assess the effects of the investigational doses of tirzepatide on pancreatic enzyme levels. Serial measures of pancreatic enzymes have limited clinical value for predicting episodes of acute pancreatitis in asymptomatic patients (Nauck et al. 2017; Steinberg et al. 2017a, b). Thus, further diagnostic follow-up of cases of asymptomatic pancreatic hyperenzymemia (lipase and/or p-amylase  $\geq 3X$  ULN) is not mandated but may be performed based on the investigator's clinical judgment and assessment of the patient's overall clinical condition. Only cases of pancreatic hyperenzymemia that undergo additional diagnostic follow-up and/or are accompanied by symptoms suggestive of pancreatitis will be submitted for adjudication.

All suspected cases of acute or chronic pancreatitis will be adjudicated by an independent clinical endpoint committee. In addition, AEs of severe or serious abdominal pain of unknown etiology will also be submitted to the adjudication committee to assess for possible pancreatitis or other pancreatic disease. Relevant data from patients with acute or chronic pancreatitis and those with severe or serious abdominal pain will be entered into a specifically designed eCRF page by study site or Lilly staff. The adjudication committee representative will enter the results of adjudication in a corresponding eCRF page.

#### **9.4.4.3. Hypersensitivity Reactions**

The investigator will report all hypersensitivity reactions either as AEs or, if any serious criterion is met, as SAEs. In the event of suspected drug hypersensitivity reactions (immediate or nonimmediate) in subjects who experience moderate to severe injection reactions as assessed by the investigator, unscheduled blood samples will be collected for PK and ADA analyses at the following time points:

- as close as possible to the onset of the event
- at the resolution of the event
- 30 ( $\pm 3$ ) days following the event.

Additionally, unscheduled serum samples for immune safety laboratory testing (including, but not limited to  $\beta$  tryptase, total immunoglobulin E, complement and cytokine panel testing) should also be collected at approximately 60 to 120 minutes and 4 to 6 weeks after the onset of the event in these subjects. Instructions for the collection and handling of blood samples will be provided by the sponsor. The actual date and time (24-hour clock time) of each sampling will be recorded.

##### **9.4.4.3.1. *Injection-site Reactions***

Injection-site assessments for local tolerability will be conducted, when reported as

- an AE from a subject, or
- a clinical observation from an investigator.

Reported injection-site reactions will be characterized within the following categories:

- edema
- erythema
- induration
- itching
- pain

All injection-site reactions reported as AEs will be closely monitored until resolution. The report of a clinically significant AE of injection-site reaction may prompt notification of the sponsor, clinical photography, and referral for dermatologic evaluation and consideration of a skin biopsy and laboratory evaluations (ALT, AST, complete blood count with absolute count for eosinophils, and additional immunogenicity testing). Investigational site staff will be provided with separate instructions/training on how to evaluate injection-site reactions and their severity in a consistent manner. Photographs of injection-site reactions may be taken in a standardized manner for record-keeping purposes; however, the photographs will not be used to evaluate the severity of injection-site reaction.

#### **9.4.4.4. Glucose Monitoring**

Site personnel will instruct patients on how to use the glucose meter provided by the site and conduct SMPG tests. In addition to the plasma glucose (PG) monitoring, patients will be educated on the symptoms of hypoglycemia and hyperglycemia. Throughout their participation in the study, patients will monitor PG levels. The site will provide patients with diaries and instructions on how to record PG results whenever the patient experiences symptoms of hypoglycemia, while not in the CRU. The investigator or designee will review PG results clinically indicative of hypoglycemia or hyperglycemia.

Additionally, site personnel will require patients who were taking OAM at screening to monitor their PG in the morning before breakfast during the lead-in period.

##### **9.4.4.4.1. Hyperglycemia and Hypoglycemia Reporting**

Episodes of hyperglycemia (fasting plasma/serum glucose  $>270$  mg/dL [15 mmol/L]) or hypoglycemia (plasma/serum glucose  $\leq 70$  mg/dL [3.9 mmol/L]) will be reported by the investigator or designated physician who will be responsible for advising the patient on what further actions to take. At their discretion, the investigator may request additional monitoring.

If the fasting plasma/serum glucose during the dosing period exceeds the acceptable level, defined as hyperglycemia on 3 or more separate days during any 2-week period between screening and the end of the dosing period, the patient will be evaluated further at the study site.

If fasting plasma/serum glucose continues to exceed the acceptable level, the investigator will discontinue the IP and initiate treatment with an appropriate antidiabetic agent. The patient will continue to be followed up in the study (for safety, PK, and immunogenicity assessment) for at least 28 days after their last dose. If hyperglycemia occurs during the follow-up period, the patient will remain in the study until completion of the planned follow-up.

Site personnel will record hypoglycemia episodes on specific eCRF pages. The investigator will treat hypoglycemia appropriately and may perform additional monitoring of plasma/serum glucose levels. The following categories of the 2017 American Diabetes Association position statement on glycemic targets (American Diabetes Association 2017) on the basis of recommendations of the International Hypoglycaemia Study Group (International Hypoglycaemia Study Group 2017) should be applied for reporting in the eCRF and evaluation of hypoglycemic events.

The main categories of hypoglycemia are outlined as follows:

**Documented Glucose Alert Level (Level 1):** plasma/serum glucose  $\leq 70$  mg/dL (3.9 mmol/L)

- **Documented symptomatic hypoglycemia:** with typical symptoms of hypoglycemia.
- **Documented asymptomatic hypoglycemia:** without typical symptoms of hypoglycemia.
- **Documented unspecified hypoglycemia:** with no information about symptoms of hypoglycemia available. (This has been called unclassifiable hypoglycemia.)

**Documented Clinically Significant Hypoglycemia (Level 2):** with similar criterion as above except for the threshold plasma/serum glucose  $< 54$  mg/dL (3.0 mmol/L)

- **Level 2 documented symptomatic hypoglycemia**
- **Level 2 documented asymptomatic hypoglycemia**
- **Level 2 documented unspecified hypoglycemia**

### **Severe Hypoglycemia (Level 3)**

- **Severe hypoglycemia (in adults):** Patients had altered mental status, and could not assist in their own care, or were semiconscious or unconscious, or experienced coma with or without seizures, and the assistance of another person required to actively administer carbohydrate, glucagon, or other resuscitative actions. Plasma/serum glucose measurements may not be available during such events, but neurological recovery attributable to the restoration of plasma/serum glucose concentration to normal is considered sufficient evidence that the event was induced by a low plasma/serum concentration (plasma/serum glucose  $\leq 70$  mg/dL [3.9 mmol/L]).
- **Severe hypoglycemia requiring medical attention:** Severe hypoglycemic events when patients require therapy by health care providers (Emergency Medical Technicians, emergency room personnel, etc.) are of particular interest to payers. Therefore, some

clinical trials may collect data on this subset of severe hypoglycemia episodes, especially if economic outcomes analyses may be based on trial results.

### Other Hypoglycemia

- **Nocturnal hypoglycemia:** Any documented hypoglycemic event (including severe hypoglycemia) that occurs at night and presumably during sleep. At Lilly, this is captured as hypoglycemia that occurs between bedtime and waking. This definition is more useful than the commonly used ~midnight to ~6 AM definition, which does not take patients' individual sleep times into consideration and is consistent with the American Diabetes Association recommendations for reporting events that occur during sleep (American Diabetes Association 2005). It is also important to collect the actual time a hypoglycemic event occurred to allow further characterization of hypoglycemia timing (for example, to allow analysis of frequency of events occurring during a 24-hr time period). Nocturnal hypoglycemia may occur at severity Levels 1, 2, or 3.
- **Relative hypoglycemia (also referred to as pseudohypoglycemia [Sequist et al. 2013]):** An event during which typical symptoms of hypoglycemia occur, that does not require the assistance of another person, and is accompanied by plasma/serum glucose  $>70$  mg/dL (3.9 mmol/L). The plasma/serum glucose value for patients with chronically poor glycemic control can decrease so rapidly that patients may report symptoms of hypoglycemia before their plasma/serum glucose concentration falls below 70 mg/dL (3.9 mmol/L). Events with plasma/serum glucose  $\leq 7$  mg/dL should not be categorized as relative hypoglycemia. Evaluation and statistical analysis of this category is optional. However, if a patient reports a relative hypoglycemic event where assistance from another person was received or the patient experienced significant symptoms, the study team should clarify the circumstances to ensure the event is not a severe hypoglycemia event and report it appropriately.
- **Probable symptomatic hypoglycemia:** Symptoms of hypoglycemia were present, but a plasma/serum glucose measurement was not reported.
- **Overall (or total) hypoglycemia:** This optional category combines most cases of hypoglycemia (documented hypoglycemia and probable symptomatic hypoglycemia, including severe hypoglycemia). It does not include relative hypoglycemia. Nocturnal and severe hypoglycemia are special cases of documented or probable hypoglycemia. If an event of hypoglycemia falls into multiple subcategories, that event should only be counted once in the category of overall (or total) hypoglycemia.

If a hypoglycemic event meets the criteria of severe, it needs to be recorded as serious in the eCRF (that is, recorded as an SAE). In the case of a hypoglycemic event (other than severe), the actual glucose value, if measured, should be recorded in the eCRF, with any treatments

administered, and not be recorded as an AE. Cases of hypoglycemia may be treated with foods rich in carbohydrates such as fruit, juice, skimmed milk, or energy bars. All episodes of hypoglycemia that are determined by the investigator to constitute severe hypoglycemia according to the definition above should be reported as SAEs.

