## 9.6 Safety and Tolerability Assessments

### 9.6.1 Adverse events

Where changes in severity are recorded in the Case Report Form (CRF), each separate severity of the AE will be reported in the listings, only the most severe will be used in the summary tables. A pre-existing condition is defined as an AE that starts before the subject has provided written informed consent and is ongoing at consent. A non-treatment emergent AE is defined as an AE which starts after informed consent but prior to dosing. A treatment-emergent AE is defined as an AE which occurs postdose or which is present prior to dosing and becomes more severe postdose.

All AEs will be listed. Treatment-emergent AEs will be summarized by treatment, severity and relationship to the study drug. The frequency (the number of AEs, the number of subjects experiencing an AE and the percentage of subjects experiencing an AE) of treatment-emergent AEs will be summarized by treatment, Medical Dictionary for Regulatory Activities (MedDRA) version 22.1 system organ class and preferred term. The summary and frequency AE tables will be presented for all causalities and those considered related to the study drug by the investigator. Any serious AEs will be listed. AEs by week of onset will be presented.

Discontinuations due to AEs will be listed.

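### Protocol 9.4.4.4.1 bars all non-severe hypoglycemia from AE recording without exception, which conflicts with the outcome-based SAE definition in 9.2.1 and can keep a serious or treatment-stopping event out of the TEAE and AE outputs

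*Protocol*

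**What the plan says.** The closing paragraph of Protocol 9.4.4.4.1 (after the Other Hypoglycemia definitions) sets two recording routes:

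- Severe events: "If a hypoglycemic event meets the criteria of severe, it needs to be recorded as serious in the eCRF", that is, as an SAE.
- All others: "In the case of a hypoglycemic event (other than severe), the actual glucose value, if measured, should be recorded in the eCRF", along with any treatment, and the event is to be "administered, and not be recorded as an AE". No exception follows.

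Severe means Level 3 in the same section: altered mental status or worse, with another person needed to give active help.

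Protocol 9.2.1 takes a different route to seriousness: "An SAE is any AE from this study that results in 1 of the following". The list that follows includes "initial or prolonged inpatient hospitalization" and important medical events. Sites must notify the sponsor of any SAE within 24 hours. Hypoglycemia is not carved out.

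For stopped treatment, Protocol 9.2 says: "If a patient's IP is discontinued as a result of an AE, study site personnel must report this to Lilly or its designee via eCRF". SAP 9.6.1 builds the TEAE tables and the serious-AE listing from AEs, and adds: "Discontinuations due to AEs will be listed". SAP 9.6.2 handles hypoglycemia separately, by category and treatment.

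**The concern.** Severity and seriousness are different things. Level 3 describes the patient's state and need for help during the episode; 9.2.1 looks at what the event led to. Protocol 9.4.4.4.1 uses the first as the gate to the second. A patient who remains alert but is admitted because of a low glucose value is not Level 3, yet meets the hospitalization criterion. One section calls that event an SAE and the other says not to record it as an AE at all.

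A patient taken off study drug for non-severe hypoglycemia has a related problem. The reporting duty in Protocol 9.2 and the discontinuation listing in SAP 9.6.1 both depend on there being an AE.

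Safety and tolerability is the primary objective, TEAE incidence is the primary endpoint, and Protocol 3.3 names hypoglycemia as a risk of the class. Whether such an event is reported quickly and counted should not depend on which section a site reads.

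**Working it through.** The plan states no figure for this point, so the main check is to follow one event through the text.

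**Case A: non-severe event that leads to admission**

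1. Is it an AE by definition? Yes. Appendix 1 defines an AE as an untoward medical occurrence, including unfavorable signs, symptoms and abnormal laboratory findings.
2. Is it an SAE under 9.2.1? Yes, by outcome.
3. Does 9.4.4.4.1 allow it to be recorded as an AE? No, because it is not Level 3. The category of severe hypoglycemia requiring medical attention does not help, since it is a subset of Level 3.
4. Result: two instructions that cannot both be followed. A site applying 9.2.1 reports within 24 hours; a site applying the more specific 9.4.4.4.1 may not.

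**Case B: non-severe event after which study drug is stopped**

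1. No AE record exists under 9.4.4.4.1.
2. The Protocol 9.2 duty and the SAP 9.6.1 listing are tied to AEs, so neither is triggered.
3. Protocol 10.2.1 reports reasons, where known, for discontinuing from the study. Protocol 9.4.4.2 and 9.4.4.4.1 show that a patient can stop study drug and stay in the study, so this need not capture the case.

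**What reaches the outputs if 9.4.4.4.1 is followed**

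| Output | Event included? |
|---|---|
| TEAE tables, SAP 9.6.1 | No |
| Serious-AE listing, SAP 9.6.1 | No |
| AE-discontinuation listing, SAP 9.6.1 | No |
| Hypoglycemia listing and summary, SAP 9.6.2 | Yes, with no seriousness or action-taken information specified |

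No rule in SAP 9.6.1 brings in events from the hypoglycemia pages.

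**Scale**

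Inputs: two cohorts, each 10 tirzepatide to 2 placebo (Protocol 10.1); placebo shown as one group across cohorts (SAP 6). Check: 2 × (10 + 2) = 24, the planned enrolment. One patient's weight in an incidence is 100/n:

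- one tirzepatide cohort: 100/10 = 10 percentage points
- both tirzepatide cohorts together: 100/20 = 5 points
- pooled placebo: 100/(2 + 2) = 25 points

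These shifts apply only if the omitted event is the patient's sole TEAE. Otherwise overall incidence is unchanged, and the loss is in the event count, the hypoglycemia preferred-term row and the two listings. The documents give no rate for such events, and I have not assumed one because the conclusion does not depend on it.

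**The case against.** The case for leaving the text alone has substance.

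- **Separate capture is a coherent design.** Dedicated pages with their own analysis avoid double counting. This stands, and the fix keeps it.
- **The events are not invisible.** SAP 9.6.2 covers Levels 1 to 3 and nocturnal, relative, probable symptomatic and overall hypoglycemia, listed and summarized by treatment. SAP 9.1 lists all databased data, and the sponsor reviews hypoglycemia during the study (Protocol 9.4.4). This stands. What is missing is any stated seriousness, or action taken with study drug, for a non-severe event.
- **The scenario is narrow.** Prior oral antidiabetic drugs are stopped in lead-in, a history of insulin therapy is largely excluded, and Protocol 3.2 reports no severe hypoglycemia in the Phase 2 experience. Protocol 8.1 has no rule that stops study drug for non-severe hypoglycemia. All of this argues for a low rate, though not zero.
- **The incidence shift may not occur.** Gastrointestinal AEs were the most frequent events in earlier studies, so an affected patient may already count as having a TEAE.

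Two stronger readings are tempting, and the documents support neither. A reader might infer that these events are certain to be lost from SAE reporting. Protocol 9.2.1 does not exempt hypoglycemia, 9.2 asks investigators to alert the sponsor to anything unusual, and 9.4.4.4.1 itself has the investigator or designated physician report episodes at or below 70 mg/dL. A site could therefore report the event correctly. A reader might also see a contradiction in Protocol 9.4.4, where the sponsor reviews "AEs including GI events, hypoglycemia, injection-site reactions, hypersensitivity reactions, and pancreatitis". Severe hypoglycemia is an SAE and so an AE, which makes that line consistent with 9.4.4.4.1.

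**Conclusion.** The point holds as a conflict between two recording rules with a foreseeable effect on the safety counts. For a non-severe event that is serious on another criterion, Protocol 9.4.4.4.1 and 9.2.1 give opposite instructions, so expedited reporting may be missed or inconsistent. If 9.4.4.4.1 is followed, that event, or one that stops study drug, is absent from TEAE incidence and from the relevant SAP 9.6.1 listings.

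The probability is low and cannot be quantified from the documents. The consequence of one case is not negligible in a study this small: up to 10 percentage points in a cohort's tirzepatide column if it is the patient's only TEAE, and an SAE or AE-discontinuation count of 1 shown as 0. These figures assume planned enrolment and that the site follows 9.4.4.4.1 over 9.2.1.

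**What to change.** In Protocol 9.4.4.4.1, reconcile the recording sentence with 9.2.1: a hypoglycemic event that is not severe is not recorded as an AE unless it meets any 9.2.1 criterion or leads to discontinuation of study drug; in those cases it is recorded as an AE or SAE in addition to the hypoglycemia page. This concerns recording only and leaves treatment and stopping decisions as they are.

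Once the AE record exists, SAP 9.6.1 picks it up without a new inclusion rule. At most, add a note that the event appears in both the AE and the hypoglycemia outputs and is counted once in each.

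The cost is one sentence in the protocol and an optional one in the SAP. The only downside is that TEAE or SAE counts may be slightly less favorable.
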